#### **7.10.1 Safety Follow Up**

Study procedures will be performed 30 days (+ 7 days) after the last dose of study medication. Patients will be contacted by telephone or visit to obtain the following information:

- Follow-up on any AEs that had not resolved by the EoT visit
- Information on any antineoplastic therapies utilized since discontinuation of ClaSPd treatment

### **7.10.2 Duration of Response and Survival Follow Up**

Every three months ( $\pm$  14 days) for 12 months after the EoT visit, if feasible and clinically appropriate, the following assessments should be obtained for patients who have not progressed to assess durability of response:

- SPEP and serum protein immunofixation
- UPEP (24-hour urine) and urine protein immunofixation
- Serum FLC
- Quantitative Ig levels
- Bone marrow aspirate, as clinically indicated, to assess progression
- Re-assessment of plasmacytomas by physical examination (if detected by physical examination at Screening)
- Skeletal survey (imaging) for bone lesions, including tumor measurements as clinically indicated to document response, at frequency determined by the Investigator

If these procedures cannot be obtained, at a minimum, a telephone call will be made to the patient (or the patient's family) every 3 months to inquire about the patient's MM status, general health, and information on any antineoplastic therapies utilized since discontinuation of study treatment.

### **7.11 Measures to Minimize Bias: Randomization and Blinding**

Not applicable.

### **7.12 Study Intervention/Follow-up Compliance**

Not Applicable.

## **8. Study Intervention Discontinuation and Participant Discontinuation/Withdrawal**

### **8.1 Discontinuation of Study Intervention**

Discontinuation from study treatment does not mean discontinuation from the study, and remaining study procedures should be completed as indicated by the study protocol. If a clinically significant finding is identified (including, but not limited to changes from baseline) after enrollment, the investigator or qualified designee will determine if any change in participant management is needed. Any new clinically relevant finding will be reported as an adverse event (AE).

The data to be collected at the time of study intervention discontinuation will include the those outlined in the EoT visit as well as the Follow Up Phase.

### **8.2 Participant Discontinuation/Withdrawal from the Study**

Participants are free to withdraw from participation in the study at any time upon request. Patients who elect to discontinue study treatment should be encouraged to continue in

the study so that follow-up information on disease progression and survival status may be obtained. However, patients may elect to withdraw consent and decline further participation in the trial. All patients will be followed until disease progression, withdrawal of consent, death or loss to follow up.

An investigator may discontinue or withdraw a participant from the study for the following reasons:

- Pregnancy
- Significant study intervention non-compliance
- If any clinical adverse event (AE), laboratory abnormality, or other medical condition or situation occurs such that continued participation in the study would not be in the best interest of the participant
- Disease progression
- If the participant meets an exclusion criterion (either newly developed or not previously recognized) that precludes further study participation
- Participant lost to follow-up after three attempts to contact subject to schedule study visit.

The reason for participant discontinuation or withdrawal from the study will be recorded on the eCRF. Subjects who sign the informed consent form but do not receive the study intervention may be replaced. Subjects who sign the informed consent form, and receive the study intervention, and subsequently withdraw, or are withdrawn or discontinued from the study, will not be replaced.

### **8.3 Lost to Follow Up**

A participant will be considered lost to follow-up if he or she fails to return for two or more visits for the beginning of a cycle and is unable to be contacted by the study site staff.

The following actions must be taken if a participant fails to return to the clinic for a required study visit:

- The site will attempt to contact the participant and reschedule the missed visit within one week and counsel the participant on the importance of maintaining the assigned visit schedule and ascertain if the participant wishes to and/or should continue in the study.
- Before a participant is deemed lost to follow-up, the investigator or designee will make every effort to regain contact with the participant (where possible, 3 telephone calls and, if necessary, a certified letter to the participant's last known mailing address or local equivalent methods). These contact attempts should be documented in the participant's medical record or study file.
- Should the participant continue to be unreachable, he or she will be considered to have withdrawn from the study with a primary reason of lost to follow-up.

### **9. Correlative/Special Studies**

Not Applicable.

## **9.1 Laboratory Correlative Studies**

Not Applicable.

## **9.2 Special Studies**

Not Applicable.

# **10. Measurement of Effect**

## **10.1 Response Criteria**

Overall response rate (ORR): the sum of partial response (PR), very good partial response (VGPR), complete response (CR) and stringent complete response (sCR), based on the IMWG response criteria (Appendix 4). Response will be assessed on day 1 of every cycle starting on cycle 2.

## **10.2 Duration of Response**

Duration of response: The duration of response is measured from the time measurement criteria for PR, VGPR, CR or sCR (whichever is first recorded) is first met until the date of progressive disease (PD) or death, whichever comes first.

## **10.3 Progression-Free Survival**

Progression-Free Survival: defined as the length of time measured from start of study treatment to PD or death, whichever comes first.

## **10.4 Other Response Parameters**

- Clinical benefit rate (CBR), defined as overall response rate (ORR) plus minimal response (MR), as defined by the IMWG criteria (Appendix 4)
- Disease control rate (DCR), defined as CBR plus stable disease (SD) for a minimum of 12 weeks
- Overall survival (OS), defined as the length of time measured from start of study treatment to death
- Minimal residual disease (MRD), as defined by the IMWG criteria (Appendix 4)
- Relative dose intensity, defined as the ratio of delivered to the planned dose intensity expressed as a percentage
- Quality of life (QOL) score, as measured by the Functional Assessment of Cancer Therapy - MM (FACT-MM) (Appendix 5)

# **11. Data Reporting / Regulatory Considerations**

## **11.1 Data Collection**

The data collection plan for this study is to utilize REDCap to capture all treatment, toxicity, efficacy, and adverse event data for all enrolled subjects.

### **11.1.1 REDCap**

REDCap (Research Electronic Data Capture) is a free data management software system that is fully supported by the Weill-Cornell Medical Center CTSC. It is a tool for the creation of customized, secure data management systems that include Web-based data-entry forms, reporting tools, and a full array of security features including user and group based privileges, authentication using institution LDAP system, with a full audit trail of data manipulation and export procedures. REDCap is maintained on CTSC-owned servers that are backed up nightly and support encrypted (SSL-based) connections. Nationally, the software is developed, enhanced and supported through a multi-institutional consortium led by the Vanderbilt University CTSA.

## **11.2 Regulatory Considerations**

### **11.2.1 Institutional Review Board/Ethics Committee Approval**

As required by local regulations, the Investigator will ensure all legal aspects are covered, and approval of the appropriate regulatory bodies obtained, before study initiation.

Before initiation of the study at each study center, the protocol, the ICF, other written material given to the patients, and any other relevant study documentation will be submitted to the appropriate Ethics Committee. Written approval of the study and all relevant study information must be obtained before the study center can be initiated or the IP is released to the Investigator. Any necessary extensions or renewals of IRB approval must be obtained for changes to the study, such as amendments to the protocol, the ICF, or other study documentation. The written approval of the IRB together with the approved ICF must be filed in the study files.

The Investigator will report promptly to the IRB any new information that may adversely affect the safety of the patients or the conduct of the study. The Investigator will submit written summaries of the study status to the IRB as required. On completion of the study, the IRB will be notified that the study has ended.

All agreed protocol amendments will be clearly recorded on a protocol amendment form and will be signed and dated by the original protocol approving signatories. All protocol amendments will be submitted to the relevant institutional IRB for approval before implementation, as required by local regulations. The only exception will be when the amendment is necessary to eliminate an immediate hazard to the trial participants. In this case, the necessary action will be taken first, with the relevant protocol amendment following shortly thereafter.

Once protocol amendments or consent form modifications are implemented at the lead site, Weill Cornell Medicine, updated documents will be provided to participating sites, as applicable. Weill Cornell Medicine must approve all consent form changes prior to local IRB submission.

Relevant study documentation will be submitted to the regulatory authorities of the participating countries, according to local/national requirements, for review and approval

before the beginning of the study. On completion of the study, the regulatory authorities will be notified that the study has ended.

#### **11.2.2 Ethical Conduct of the Study**

The Investigators and all parties involved should conduct this study in adherence to the ethical principles based on the Declaration of Helsinki, GCP, ICH guidelines and the applicable national and local laws and regulatory requirements.

This study will be conducted under a protocol reviewed and approved by the applicable ethics committees and investigations will be undertaken by scientifically and medically qualified persons, where the benefits of the study are in proportion to the risks.

#### **11.2.3 Informed Consent**

The investigator or qualified designee must obtain documented consent according to ICH-GCP and local regulations, as applicable, from each potential subject or each subject's legally authorized representative prior to participating in the research study. Subjects who agree to participate will sign the approved informed consent form and will be provided a copy of the signed document.

The initial ICF, any subsequent revised written ICF and any written information provided to the subject must approved by IRB prior to use. The ICF will adhere to IRB requirements, applicable laws and regulations.

#### **11.2.4 Compliance with Trial Registration and Results Posting Requirements**

Under the terms of the Food and Drug Administration Modernization Act (FDAMA) and the Food and Drug Administration Amendments Act (FDAAA), the Sponsor-Investigator of the trial is solely responsible for determining whether the trial and its results are subject to the requirements for submission to <http://www.clinicaltrials.gov>. Information posted will allow subjects to identify potentially appropriate trials for their disease conditions and pursue participation by calling a central contact number for further information on appropriate trial locations and trial site contact information.

#### **11.2.5 Record Retention**

Essential documents are those documents that individually and collectively permit evaluation of the study and quality of the data produced. After completion of the study, all documents and data relating to the study will be kept in an orderly manner by the Investigator in a secure study file. Essential documents should be retained for 2 years after the final marketing approval in an ICH region or for at least 2 years since the discontinuation of clinical development of the IP. In addition, all subjects medical records and other source documentation will be kept for the maximum time permitted by the hospital, institution, or medical practice.

### **12. Statistical Considerations**

#### **12.1 Study Design/Endpoints**

A Simon's two-stage design (Simon, 1989) will be used. The null hypothesis that the true ORR is  $\leq 35\%$  will be tested against a one-sided alternative that the true ORR  $\geq 60\%$  (see Background section for further details regarding a pooled estimate of the ORR in studies of pomalidomide-containing two- and three-drug regimens).

Tabulations will be produced for appropriate disposition, demographic, baseline, efficacy and safety parameters. For categorical variables, summary tabulations of the number and percentage of patients within each category (with a category for missing data) of the parameter will be presented, as well as 95% confidence intervals (CI), unless otherwise stated. For continuous variables, the number of patients, mean, median, standard deviation (SD), minimum, and maximum values will be presented. Time-to-event data will be summarized using Kaplan-Meier methodology using 25th, 50th (median), and 75th percentiles with associated 95% CI, as well as percentage of censored observations.

The analysis will be performed on an intent-to-treat population, consisting of all patients who receive at least one dose of the study treatment. This population will include patients who have discontinued therapy due to toxicity or disease progression and patients who have died from any cause, including those related to study drug or disease. This population will be used for the analyses of both efficacy and safety.

Demographic characteristics will include gender, race, ethnicity (Hispanic/non-Hispanic origin), and age at time of consent. For gender, race, and ethnicity, the summary statistics will be the number and percentage of patients within each category. For age at time of consent, the mean, median, minimum, maximum, and standard deviation will be provided for each group and the total sample. Baseline characteristics include ECOG Performance Status, duration from initial diagnosis, response to previous therapy, types of prior therapy, and height/weight. Baseline data will be tabulated for the same categories as used for demographics, using summary statistics. Medical history and physical examination results at baseline will be tabulated by cohort.

## **12.2 Sample Size/Accrual Rate**

In the first stage, 18 patients will be accrued. If there are 6 or fewer responses in these 18 patients, the study will be stopped. Otherwise, 8 additional patients will be accrued for a total of 26. The null hypothesis will be rejected if 14 or more responses are observed in 26 patients. This design yields a one-sided type I error rate of 0.05 and power of 0.8 when the true ORR is 60%.

## **12.3 Stratification Factors**

Not applicable.

## **12.4 Analysis of Endpoints**

### **12.4.1 Analysis of Primary Endpoints**

The analysis of Overall Response Rate (ORR) will be performed by calculating the point estimate of the percentage of patients who have a response of SCR, CR, VGPR or PR, as assessed by IMWG criteria. A 95% CI for the ORR will be calculated using exact methods and presented for descriptive purposes.

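### Does the 95% exact confidence interval for the response rate contradict the one-sided 5% rule that 14 of 26 responses is a success?

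*Combined protocol and SAP*

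**What the plan says.** Section 12.1 sets up a Simon two-stage design in which a null ORR of at most 35% "will be tested against a one-sided alternative that the true ORR" is at least 60%. Section 12.2 gives the futility rule, "If there are 6 or fewer responses in these 18 patients, the study will be stopped", then the final rule after 8 further patients: "The null hypothesis will be rejected if 14 or more responses are observed in 26 patients". The same count rule stands in the Protocol Summary and in section 3.1. On operating characteristics, section 12.2 states: "This design yields a one-sided type I error rate of 0.05", together with "power of 0.8 when the true ORR is 60" percent.

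Section 12.4.1 plans a point estimate of the ORR and one interval: "A 95% CI for the ORR will be calculated using exact methods and presented for descriptive purposes". It does not say whether that interval is two-sided. Section 12.1 makes 95% the default level for categorical summaries, and section 12.4.3 specifies two-sided 95% exact intervals for the clinical benefit rate and the disease control rate, so two-sided is the natural reading.

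**The concern.** The test and the interval work at different error levels. A one-sided 5% test corresponds to a lower confidence bound with 5% below it; a two-sided 95% interval puts only 2.5% there. At the smallest winning result the report could therefore say that 35% is rejected and print beside it an interval that includes 35%. This is the only precision statement planned for the primary endpoint, and section 12.4.1 does not repeat the cut-off or the 35% reference.

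If readers judged success by whether the interval excludes 35%, they would in effect be using a cut-off of 15, with power at 60% well below the planned 0.80. Separately, section 12.2 presents 0.05 as what the design delivers, and an exact calculation gives a smaller number, which suggests a design figure that was not computed.

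**Working it through.** **Inputs.** Null rate 0.35 and alternative 0.60 (section 12.1). Stage 1: 18 patients, stop at 6 or fewer responses. Stage 2: 8 more patients, reject at 14 or more of 26. One-sided 0.05 and power 0.8 (section 12.2). Exact 95% interval (section 12.4.1), read as two-sided Clopper-Pearson.

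**Step 1: reproduce the design.** With X1 ~ Bin(18, p) and X2 ~ Bin(8, p),

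P(reject | p) = Σ over x = 7 to 18 of P(X1 = x) · P(X2 ≥ 14 − x).

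- At p = 0.35 this is 0.0377.
- At p = 0.60 it is 0.8004, which matches the stated power.
- With a cut-off of 13 the value at p = 0.35 is 0.0825, above 0.05. With 15 it is 0.0150, and power at 60% falls to 0.674.

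So 14 is the lowest cut-off that keeps the type I error within 0.05, and it is also the one that keeps power at 0.80. A search over total sizes 20 to 32, requiring type I error at most 0.05 and power at least 0.80, returns this same design (6/18, then reject above 13/26) as the minimax Simon design. The 0.05 is the constraint that produced the design. Response counts are discrete, so the attained level falls below the limit.

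**Step 2: the intervals around the cut-off.** For x responses in n = 26, the lower limit is the α/2 quantile of Beta(x, n − x + 1) and the upper limit is the 1 − α/2 quantile of Beta(x + 1, n − x).

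| Responses | Decision by count | 95% interval | 90% interval |
|---|---|---|---|
| 13/26 | not rejected | 29.9% to 70.1% | 32.7% to 67.3% |
| 14/26 | rejected | 33.4% to 73.4% | 36.2% to 70.8% |
| 15/26 | rejected | 36.9% to 76.6% | 39.8% to 74.2% |

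The result at 14/26 does not depend on the type of exact interval. A lower limit that allows for the two stages is also 33.4%, and a Sterne interval runs from 34.4% to 71.8%.

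**Step 3: why 14 is the only such count.** The tail probability of 14 or more at 35% is 0.0377. That lies between 0.025 and 0.05, so a one-sided 5% rule rejects while a two-sided 95% interval keeps 35%. At 15 the tail is 0.0150, below both levels, and the interval lies above 35%. At 13 it is 0.0825, above both, and the lower limit is below 35%; at smaller counts the lower limit is lower still. Test and interval therefore point different ways at one count.

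**Step 4: how often that count occurs.** P(total = 14, trial not stopped at stage 1) = P(≥ 14) − P(≥ 15).

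- True ORR 60%: 0.8004 − 0.6737 = 0.127, or 0.127 / 0.800 = 16% of successes.
- True ORR 55%: 0.154, 25% of successes.
- True ORR 50%: 0.144, 34% of successes.

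These are probabilities of observing one particular count. They are not rates of wrong conclusions.

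**Step 5: does any rule in the plan use the interval?** The Protocol Summary, section 3.1 and section 12.2 all define rejection by the count. Section 12.4.1 gives the interval a descriptive role. No section makes success depend on the interval excluding 35%. At 14/26 the plan gives one answer: reject.

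**The case for a change.** The strongest opposing case is that calling the interval descriptive lessens the awkwardness without removing it. A results table built from section 12.4.1 alone would show 53.8% (33.4% to 73.4%) with nothing to explain why the null was rejected, and an explanation written after the result would look post hoc. The outcome is not rare. A two-sided 90% interval would agree with the rule on both sides of the cut-off and costs one sentence. Section 12.2 also puts a nominal figure (0.05) and an attained one (0.80) in the same sentence.

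The arithmetic behind all of this stands. What does not follow is that the plan is wrong. The explanation at 14/26 would not be post hoc, because the count rule is already written in three places. The 95% interval has valid coverage as an estimate, and it matches the default in section 12.1 and the level used for the related response rates in section 12.4.3. Choosing 90% for the primary endpoint is a legitimate reporting preference, but it changes no decision, error rate or power. Stating the attained 0.038 beside the 0.05 would be more exact wording, and it would correct no cut-off. The difference is on the safe side: false positives are rarer than the stated figure implies.

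**Conclusion.** The concern does not hold. Rejection is defined by 14 or more responses in 26, and that rule controls the one-sided type I error at 0.05 (attained 0.0377) with power 0.8004 at 60%. The descriptive 95% interval includes 35% at one successful count, 14/26, and the plan's conclusion there is unambiguous and sound. Sample size, both bounds and power reproduce.

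This rests on three readings: that the interval in section 12.4.1 is two-sided, as its usual meaning and section 12.4.3 suggest; that the 0.05 in section 12.2 is the nominal limit; and that the descriptive label is respected, so that nobody uses the interval as a second test. If the interval were meant as a one-sided 95% bound, its lower limit at 14/26 would be 36.2% and even the apparent mismatch would vanish.

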#### **12.4.2 Analysis of Secondary Endpoints**

Safety analyses will be performed using data available from all patients who receive  $\geq 1$  dose of the study treatment. Adverse Events (AEs) will be coded using the Medical Dictionary for Regulatory Activities (MedDRA) dictionary and displayed in tables and listings using System/Organ/Class (SOC) and Preferred Term. Analyses of AEs will be performed for those events that are considered to be treatment emergent AEs (TEAEs), defined as any AE with onset or worsening of a pre-existing condition on or after the first administration of study medication through 30 days following last dose or any event considered drug-related by the Investigator through the end of the study. AEs with partial dates will be assessed using the available date information to determine if treatment-emergent; AEs with completely missing dates will be assumed to be treatment-emergent.

AEs will be summarized by patient incidence rates. In all tabulations, a patient may contribute only once to the count for a given AE preferred term. The number and percentage of patients with TEAEs will be summarized, as well as the number and percentage of patients with TEAEs assessed by the Investigator as at least possibly related to treatment. The number and percentage of patients with any Grade  $\geq 3$  TEAE will be tabulated in the same manner. In the event that a patient experiences repeated episodes of the same TEAE, the event with the highest severity and/or strongest causal relationship to study treatment will be used for purposes of tabulations. Serious AEs (SAEs) will also be tabulated. No formal hypothesis-testing analysis of AE incidence rates will be performed.

All AEs (treatment emergent and post-treatment) will be listed in patient data listings. Separate by-patient listings will be provided for the following: patient deaths, SAEs, and AEs leading to withdrawal.

The actual value and change from baseline for each on study evaluation will be summarized for each clinical laboratory parameter, including hematology and clinical chemistry, and for all study patients combined. In the event of repeat values, the last non-missing value per study day/time will be used. Severity of select clinical lab measures will be determined using CTCAE criteria (i.e., those measures that have a corresponding CTCAE grade classification). Labs with CTCAE Grades  $\geq 3$  will be presented in a data listing. Shift tables that present changes from baseline to worst on-study values relative to CTCAE classification ranges will be produced.

The actual value and change from baseline to each on-study evaluation will be summarized for vital signs for all study patients combined. By-patient listings of vital sign measurements will be presented in data listings.

Physical examination results at screening will be summarized; all other abnormal physical examination data were to be recorded on the AE eCRF. All examination findings will be presented in a data listing.

The use of concomitant medications will be included in by-patient data listings.

